# **Research Protocol Summary**

TITLE:	A realist evaluation of 'paste' and 'dry' compression bandages
Short title:	ROSE study
IRAS number	328315
R&D No	10604
Study design	Realist evaluation
Research Question	When, for whom and in what circumstances are two different types of compression bandages selected in the treatment of lower limb ulceration?
Objectives	To understand when, for whom and in what circumstances are two different types of compression bandages selected; to add to the body of knowledge that pertains to leg ulceration care and guide staff to select the appropriate compression bandage for each patient.
Patient population	Patients with bilateral leg ulceration who are in existing compression bandages or are about to be started with compression bandages.
Patients Sample size	40 patients
Sponsor	The Newcastle upon Tyne Hospitals NHS Foundation Trust
Founder	Milliken Healthcare Products, LLC ("Milliken")
Chief Investigator	[name]
Co-investigators	Research Nurse [name], [name], [name]
Organisations where research will take place	The Newcastle upon Tyne Hospitals NHS Foundation Trust
Planned timeline	Study start date: 1 December 2024 Study end date: 1 April 2026
Protocol version, date	Version 2.3 18 December 2024

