# Participant inclusion/exclusion criteria

Patient Inclusion

- Age  $\geq$  18 years of age
- Patient living in Newcastle upon Tyne, with a Newcastle GP.
- Patients with **existing** bilateral leg ulceration or legs that require compression bandages to prevent ulcer (re)-occurrence.
- Patients with **new** bilateral leg ulceration or legs that require compression bandages to prevent ulcer (re)-occurrence.

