# **Recruiting and Screening**

Patients will be existing patients on the Newcastle upon Tyne Hospitals NHS Foundation Trust District Nursing's workload. Potential patients participants will be identified using Systm1, the electronic documentation system used by District Nurses in Newcastle. A list of potential participants will be drawn by the administrative team within District Nurses.

During the course of standard care, District Nurses will ask permission for the Research Nurse to contact them via telephone, letter or email. With agreeing, the District Nurse will enter the following text in the patient electronic documentation: "Mr/Mrs/Ms [Patient name] has agreed for the Research Nurse to contact him/her regarding the ROSE study". Upon contact, the Research Nurse will give potential patient participants the PIS and seek informed consent.

Thus Nurse participants will be involved in the recruitment process, and it is hoped that this will enhance their willingness to be recruited to the study alongside their patients.

Nurse Participants will be contacted by the Research Nurse who is a NuTH employee, through the existing nursing management structure.

In accordance with Good Clinical Practice, participation in this study is voluntary and any decision not to participate will not have any impact on how the subject's clinical treatment is performed. Patients will have a minimum of 24h to decide whether to participate or until the following visit by the District Nurses team (compression bandages are changed 2-3 times per week).

Following recruitment, a participant will be considered enrolled once he/she signs and dates the informed consent form. Once enrolled, the participant will be assigned a unique subject number, which will not contain information that could identify him/her (such as name or date of birth). The unique participant number will be used to label study data throughout the study.

All District Nurses in the organisation will be sent the Patient Information Sheet by their managers so that they will be well informed about the study aim and objectives. The research nurse might observe the application of compression bandaging. Patients receive care by a group of District Nurses, it is not unusual for patients to see 10-12 different District Nurses during the course of their treatment. Nurse participation is voluntary.

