# Compression bandage selection procedure

The choice to apply 'full compression' versus 'reduced compression' will be dictated by the aetiology of the ulcer, wound assessment etc as per standard care. However, one leg will be bandaged in 'paste' compression and one leg in 'dry' compression, through a process of randomisation, using pre-prepared sealed envelopes.

The two types of compression bandages that will be used in this study are 'standard care' and are:

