# Safety

There is no anticipated personal safety risk associated with taking part in this study. Appropriate precautions are in place to ensure medical and personal information is kept safe through adhering to appropriate governance regulations.

Participants will be allocated compression bandages that are used for its intended licensed purpose, are considered standard care in the Trust and that are available via NHS procurement routes.

Apart from being allocated to a different type of compression bandage per leg, all patients will be commenced on a compression therapy; therefore, all patients will receive the indicated clinical care they would receive if they were not in the study; they will be cared for in exactly the same manner as they normally would bar that usually both legs would be compressed using the same product for ease of procurement. However, in standard care, it is not unusual to be prescribed two different brands of compression bandages. Some bandage types may be more comfortable at controlling symptoms such as pruritus.

Participants cannot claim payments, reimbursement of expenses or any other benefits or incentives for taking part in this research.

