# **APPENDIX 3. PATIENT AND NURSE'S EXPERIENCE** PATIENT AND NURSE QUESTIONNAIRE – CLINICAL EXPERIENCE

Bandage used: Right Leg S1F/S1R, S2F/S2R or S3F/ S3R (circle what applies)	S1F = UrgoK2 S1R = UrgoK2 Lite S2F = Coban2 S2R = Coban2 Lite S3F = AndoFlex TLC Calamine S3R = AndoFlex TLC Lite Zinc
FOR THE PATIENT TO COMPLETE	
Please rate the following as your overall experience of circle):	of wearing this bandage (please
Has this bandage helped with your pain?	Yes No N/a
Has this bandage improved your comfort?	Yes No N/a
Has this bandage improved your ability to wear normal footwear and clothes?	Yes No N/a
Has this bandage stayed in place?	Yes No N/a
Has this bandage improved your skin condition?	Yes No N/a
Has this bandage improved your skin irritation?	Yes No N/a
Please add any further comment of your personal experience	
FOR THE NURSE TO COMPLETE	
Prior to last bandage application, was the leg washed with Hydromol mixed in warm water?	Yes No N/a
Prior to last bandage application, was the leg debrided using a debridement cloth or tenatome?	Yes No N/a
Looking at the leg, has this bandage helped improve the leg's skin condition?	Yes No N/a
Looking at the leg, has this bandage reduced the leg's skin irritation?	Yes No N/a
Looking at the leg, has this bandage helped with wound healing?	Yes No N/a

Looking at the leg, has this bandage helped with wound

malodour?

Yes

No N/a

	S1F = UrgoK2
	S1R = UrgoK2 Lite
Bandage used: Left Leg	
	S2F = Coban2
S1F/S1R, S2F/S2R or S3F/ S3R (circle what applies)	S2R = Coban2 Lite
	S3F = AndoFlex TLC Calamine
	S3R = AndoFlex TLC Lite Zinc

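### For patients already in compression, continuing or switching bandage is tied to paste or dry, and the baseline form does not record what is needed to separate the two

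*Protocol*

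**What the plan says.** The Research Protocol Summary takes in "Patients with bilateral leg ulceration who are in existing compression bandages or are about to be started with compression bandages". The inclusion criteria likewise accept existing and new cases of "bilateral leg ulceration or legs that require compression bandages to prevent ulcer (re)-occurrence". Under Recruiting and Screening, "Patients will be existing patients on the Newcastle upon Tyne Hospitals NHS Foundation Trust District Nursing's workload". The Timeline section starts at Week 0 and describes no run-in.

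On what these patients wear before entry, the Safety section says that "usually both legs would be compressed using the same product for ease of procurement", then adds that "in standard care, it is not unusual to be prescribed two different brands of compression bandages". The study systems are the Trust's own: "The two types of compression bandages that will be used in this study are 'standard care".

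On allocation, the Compression bandage selection procedure says "one leg will be bandaged in 'paste' compression and one leg in 'dry' compression, through a process of randomisation, using pre-prepared sealed envelopes". The Timeline section instead has each leg randomised among three systems: S1 and S2 (both dry) and S3 (paste).

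On outcomes, the patient form in Appendix 3 asks change questions leg by leg, for example "Has this bandage improved your comfort", and states no reference point. The nurse application form asks for ratings relative to the system used before. Table 1 schedules these forms at Weeks 1, 4 and 8 only. Appendix 1 lists place and frequency of care, dressing and skin-care product, but neither the bandage worn before entry nor whether the patient is new to compression.

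**The concern.** Two legs of one person make a good comparison because most things are shared. Here something is not shared. If both legs wore the same product at entry, giving one leg paste and the other dry means that at least one leg must change, and the prior product decides which leg can stay the same. Randomising left against right does not remove this, because the link runs through bandage type and not through side.

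A question about whether a bandage has improved something can be read as a change from a different bandage on the switched leg, and as experience of a familiar one on the continued leg. The nurse rating has the same difficulty: on a continued leg the comparator may be the product being rated.

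The Protocol's premise is that the systems work equally well, and it expects the findings to shape guidance on bandage selection. The experience items therefore carry much of the evidence. If prior product is not collected, no later analysis plan can separate a paste-or-dry difference from a switched-or-continued one.

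**Working it through.** The Protocol gives 40 patients without an effect size, power or dropout rate, so it has no figure of its own to reproduce. The check enumerates the allocations.

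**Inputs**
- 40 patients (Sample and recruitment).
- S1 and S2 are dry and S3 is paste (Compression bandage selection procedure).
- The same system is on both legs before entry, which the Safety section calls usual.
- Assumption: the dry leg is split evenly between S1 and S2. No ratio is stated.
- Assumption: continuing is judged by system, ignoring full or reduced strength.

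**Step 1. One paste leg and one dry leg**

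| Prior system, both legs | Paste leg continues | Dry leg continues | Exactly one leg continues | Neither continues |
|---|---|---|---|---|
| S3 | 1 | 0 | 1 | 0 |
| S1 or S2 | 0 | 1/2 | 1/2 | 1/2 |

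Both legs can never continue.

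**Step 2. The Timeline section's allocation**
- Two different systems out of three: two of the three possible pairs contain the prior system, so exactly one leg continues with probability 2/3 = 67%.
- Each leg independent at 1/3: exactly one continues with probability 2 × 1/3 × 2/3 = 4/9 = 44%. Both continue with 1/9 = 11% and neither with 4/9 = 44%.

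Across all readings, 44% to 100% of patients who wore one study system on both legs have exactly one continued leg.

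**Step 3. Illustration of the count, under Step 1**

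Let e be the share of existing users. Let d be the share of those wearing one dry study system on both legs, with the rest in S3 on both legs. The Protocol gives neither share. Take e = 0.75 and d = 0.80.
- Continue dry only: 40 × e × d × 0.5 = 40 × 0.75 × 0.80 × 0.5 = 12.
- Continue paste only: 40 × e × (1 − d) = 40 × 0.75 × 0.20 = 6.
- Unlike pairs: 12 + 6 = 18. Net imbalance: 12 − 6 = 6.
- The other 22: 12 with both legs switched and 10 new to compression.

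**Step 4. Where the imbalance reverses**

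Set 0.5d = 1 − d, which gives d = 2/3. At d = 0.60 and e = 0.75, dry only is 40 × 0.75 × 0.60 × 0.5 = 9 and paste only is 40 × 0.75 × 0.40 = 12. Most existing users then wear dry, yet continued paste legs are the more numerous.

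**Step 5. Range when some prior products fall outside the pattern**

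Let s be the share of existing users in one study system on both legs. The number of unlike pairs lies between 40 × e × s × 0.5 (all prior dry) and 40 × e × s (all prior paste).

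| e | s | Unlike pairs of 40 |
|---|---|---|
| 0.25 | 0.50 | 2.5 to 5 |
| 0.50 | 0.75 | 7.5 to 15 |
| 1 | 1 | 20 to 40 |

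**The case against.** The strongest reply is that the case mix is not in the Protocol. A reader might infer that one leg often keeps its old bandage. That is an inference: the 44% to 100% applies only to patients who wore one study system on both legs, and their share of the 40 is unknown. New starters are unaffected. Patients whose prior product is outside S1 to S3 switch both legs. The Safety section also says that two brands on one patient are not unusual, and those patients do not fit the pattern in the same way. All of this stands.

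Other tempting readings go too far:
- That a mainly dry case mix must favour paste. The balance of continued legs turns at two-thirds dry, not one-half. The answer expected on a continued leg is also unproven: a patient content with a familiar bandage could say yes as readily as no.
- That 12 of 40 measures the bias. It leaves out the 6 paste users who pull the other way.
- That the Data analysis section, by analysing the data together, commits to pooling new and existing users. The sentence is about combining data sources into themes, and subgroup reporting may sit in an analysis plan not shown.
- That the contrast between new and existing patients is lost. Status has to be considered at screening and may be recoverable from the electronic record. But the Protocol plans no field for it, and eligibility status would not give the prior product.

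Finally, this is a descriptive realist evaluation with no hypothesis test, and each leg has a free-text comment. The item on the bandage staying in place is not a change question. The harm is therefore to interpretation, not to an error rate. None of this supplies the missing baseline information.

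**Conclusion.** The point holds as a limit on interpreting the leg-to-leg experience results. For patients who wore one study system on both legs, the selection procedure ties continuing or switching to bandage type: all prior paste users have exactly one continued leg, and so do half of prior dry users if the dry brands are split evenly. Under the Timeline section's allocation the figure is 67% or 44%. The two sections describe the allocation differently and must be reconciled.

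The number of patients affected and the direction of any distortion cannot be stated from the Protocol. The 18 unlike pairs and net 6 are illustrative, and rest on 75% existing users, 80% of them in dry, all with one study system on both legs. What is fixed badly here is the data collection: without prior product and new or existing status, the effect can be neither described nor ruled out.

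**What to change.** 1. In Appendix 1, at Week 0 and for each leg, record whether compression is new or existing, the prior product, and whether the allocated product is the same one.
2. In Appendix 3, beside the change items, add a current-state item per leg, such as how comfortable the bandage is now, so that a continued and a switched leg can be scored on the same footing.
3. Report the leg-level paste and dry results for all patients, and split by new to compression, both legs switched, and one leg continued (by prior product).
4. Keep every group in the conclusion. Resting it on new and both-switched patients alone would, under the one-paste, one-dry allocation, remove every patient who entered with S3 on both legs. Any both-switched patients from a study system would then all be former dry users.
5. Reconcile the allocation wording in the Compression bandage selection procedure and Timeline sections.

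The cost is a few extra fields, one added item per leg and one further table split. The subgroup counts will be small and should be read descriptively. Nothing in patients' care changes.

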# **Study Protocol**

# **Project summary**

This study aims to provide explanations of when, for whom and in what circumstances are two different types of compression bandages (paste or dry) selected in the treatment of lower limb ulceration.

Compression bandages are used in the treatment of leg ulceration. A leg ulcer develops when blood vessels are not working as they should; they are painful, distressing and have a considerable impact on quality of life. They require frequent dressing changes, but with correct treatment can heal within three months. Evidence that compression is the gold standard to heal leg ulceration exists, but comparative data between different brands of compression bandages does not. Selection of a compression system is often based on nurses' preference, based on their acquired knowledge and skills of product application. This study aims to understand when, for whom and in what circumstances two very different product types should be selected to treat individual patient's lower limbs.

Patients have been the primary inspiration for this project. They often report that they are unable to tolerate compression bandages and when questioned in more detail, it appears that different systems have not been considered.

This study will use a research technique called 'realist evaluation', which acknowledges that leg ulcer care is complex, and is undertaken in a complex health care system. The process commences with listing what we think is happening (initial theories) and refine this through the analysis until the most plausible explanation is found.

The study is divided into two concurrent parts:

Patients who require bilateral compression bandages (registered with a Newcastle upon Tyne GP) will be selected from the caseload of District Nurses and Ambulatory Clinics.

- Opinions on the ease of application will be sought from Community Nurses and District Nurses who are applying the compression bandages to the recruited patients
- (ii) Opinions on comfort will be sought from the recruited patients.

# **Background information**

Venous leg ulcers affect 1.5% of the population and 3% of people aged over 80. They are painful, distressing and have a considerable impact on quality of life. They restrict day-today living including working, shopping, cooking, and socialising with family and friends. Leg ulcers develop from a range of comorbidities, such as venous or arterial disease, heart failure, rheumatoid arthritis but also through traumatic incidents like skin tears or insect bites. Most people with leg ulcers are treated by nurses; compression bandages are the gold standard for treatment (SIGN 2010). The financial burden placed on the NHS for leg ulceration has been estimated at £3.2 billion per year.

Additionally, compression bandages are also used to prevent leg ulceration, for instance after traumatic incidents where skin tears have been sustained or in chronic oedema, due to cardiac failure or after a leg ulcer has healed, to prevent re-occurrence.

There are a whole range of compression bandages on the market. In the 2022-2023 financial year, in the Newcastle upon Tyne Hospitals NHS Foundation Trust, the cost of compression bandages was in excess of 171k (159k in community care and 12k in acute care). Ensuring that the correct bandage to maximise healing for this patients' group is a national priority.

This study is concerned with understanding when, for whom and in what circumstances are two different types of compression bandages selected in the treatment of lower limb ulceration.

#### Research question and study aim

This research asks: 'When, for whom and in what circumstances are two different types of compression bandages selected in the treatment of lower limb ulceration?'

This study aims to provide explanations of when, for whom and in what circumstances are two different types of compression bandages selected in the treatment of lower limb ulceration. The premise is that all systems under review in this study work equally well, but it is unclear which system works best in the right patient, at the right time and in the hand of the right clinician.

The secondary objectives are to add to the body of knowledge that pertains to leg ulceration care and guide staff to select the right compression bandage for each patient.

#### **Theoretical framework**

A realist evaluation will be undertaken, which contends that intervention impacts (Outcomes) occur when certain causal processes (Mechanisms) are 'triggered' in the most favourable environments (Contexts). CMO configurations are used as explanatory theories that are refined and tested with empirical data.

# Study Design Developing Initial Programme Theories (IPTs)

A key element in realist synthesis is the formulation of 'educated guesses' theories, which are explanatory statements based on the available literature, in addition to the researcher team clinical expertise and experience. An initial meeting will take place prior to the beginning of the study with 1 District Nurse, 1 TVN (community); 1 Registered Nurse from the Ambulatory Clinics and the research team to develop these initial statements and they will be refined by the research team into Initial Programme Theories. These IPTs will be tested and refined with data collected below.

#### Sample and recruitment

#### a) Patient recruitment

40 patients will be recruited for having bilateral leg ulceration and being treated in compression bandages or being in compression bandages for the prevention of leg ulceration (re-)occurrence.

# b) Nurse recruitment

The nurses who are applying the compression bandages to the recruited patients will be asked questions about the ease of application. It is not possible to estimate how many nurses will be recruited, as a number of nurses will be looking after the above 40 patients, as per standard care.

- Nursing questionnaire for comfort at application, during wear and on removal, fluid handling (see Appendix 3)
- Nursing questionnaire asking ease of use/application (see Appendix 3).

# Participant inclusion/exclusion criteria

Patient Inclusion

- Age  $\geq$  18 years of age
- Patient living in Newcastle upon Tyne, with a Newcastle GP.
- Patients with **existing** bilateral leg ulceration or legs that require compression bandages to prevent ulcer (re)-occurrence.
- Patients with **new** bilateral leg ulceration or legs that require compression bandages to prevent ulcer (re)-occurrence.

# Patient Exclusion

- Patient younger < 18 years of age
- Patients in nursing homes
- Patients with leg ulcerations that do not necessitate compression bandages.
- Patients with leg ulcerations that require a specific type of compression bandages (i.e. lymphoedema)

# Nurse Inclusion

- Registered Nurse bandaging the recruited patient participant.

#### Nurse Exclusion

- Nurse associate (NA)
- Assistant practitioner (AP)
- Healthcare assistant (HCA)

# **Recruiting and Screening**

Patients will be existing patients on the Newcastle upon Tyne Hospitals NHS Foundation Trust District Nursing's workload. Potential patients participants will be identified using Systm1, the electronic documentation system used by District Nurses in Newcastle. A list of potential participants will be drawn by the administrative team within District Nurses.

During the course of standard care, District Nurses will ask permission for the Research Nurse to contact them via telephone, letter or email. With agreeing, the District Nurse will enter the following text in the patient electronic documentation: "Mr/Mrs/Ms [Patient name] has agreed for the Research Nurse to contact him/her regarding the ROSE study". Upon contact, the Research Nurse will give potential patient participants the PIS and seek informed consent.

Thus Nurse participants will be involved in the recruitment process, and it is hoped that this will enhance their willingness to be recruited to the study alongside their patients.

Nurse Participants will be contacted by the Research Nurse who is a NuTH employee, through the existing nursing management structure.

In accordance with Good Clinical Practice, participation in this study is voluntary and any decision not to participate will not have any impact on how the subject's clinical treatment is performed. Patients will have a minimum of 24h to decide whether to participate or until the following visit by the District Nurses team (compression bandages are changed 2-3 times per week).

Following recruitment, a participant will be considered enrolled once he/she signs and dates the informed consent form. Once enrolled, the participant will be assigned a unique subject number, which will not contain information that could identify him/her (such as name or date of birth). The unique participant number will be used to label study data throughout the study.

All District Nurses in the organisation will be sent the Patient Information Sheet by their managers so that they will be well informed about the study aim and objectives. The research nurse might observe the application of compression bandaging. Patients receive care by a group of District Nurses, it is not unusual for patients to see 10-12 different District Nurses during the course of their treatment. Nurse participation is voluntary.

